8.1.8.1 Timing of Dose Administration

Study intervention will be administered orally BID, approximately 12 hours apart for approximately 52 weeks during the treatment period.

8.1.9 Discontinuation and Withdrawal

Participants who discontinue study intervention prior to completion of the treatment period should be encouraged to continue to be followed for all remaining study visits.

When a participant withdraws from participation in the study, all applicable activities scheduled for the discontinuation visit should be performed (at the time of withdrawal). Any AEs that are present at the time of withdrawal should be followed in accordance with the safety requirements outlined in Section 8.4 .

8.1.9.1 Withdrawal From Future Biomedical Research

Participants may withdraw their consent for future biomedical research. Participants may withdraw consent at any time by contacting the principal investigator for the main study. If medical records for the main study are still available, the investigator will contact the Sponsor using the designated mailbox ([contact]). Subsequently, the participant's consent for future biomedical research will be withdrawn. A letter will be sent from the Sponsor to the investigator confirming the withdrawal. It is the responsibility of the investigator to inform the participant of completion of withdrawal. Any analyses in progress at the time of request for withdrawal or already performed prior to the request being received by the Sponsor will continue to be used as part of the overall research study data and results. No new analyses would be generated after the request is received.

In the event that the medical records for the main study are no longer available (eg, if the investigator is no longer required by regulatory authorities to retain the main study records) or the specimens have been completely anonymized, there will no longer be a link between the participant's personal information and their specimens. In this situation, the request for specimen withdrawal cannot be processed.

8.1.10 Participant Blinding/Unblinding

STUDY INTERVENTION IDENTIFICATION INFORMATION IS TO BE UNMASKED ONLY IF NECESSARY FOR THE WELFARE OF THE PARTICIPANT. EVERY EFFORT SHOULD BE MADE NOT TO UNBLIND.

For emergency situations where the investigator or medically qualified designee needs to identify the drug used by a participant and/or the dosage administered, he/she will contact the emergency unblinding call center by telephone and make a request for emergency unblinding. As requested by the investigator or medically qualified designee, the emergency unblinding call center will provide the information to him/her promptly and report unblinding to the Sponsor. Prior to contacting the emergency unblinding call center to request unblinding of a participant's treatment assignment, the investigator or medically qualified designee should make reasonable attempts to enter the intensity of the AEs observed, the relation to study intervention, the reason thereof, etc., in the medical chart. If it is not possible to record this assessment in the chart prior to the unblinding, the unblinding should not be delayed.

In the event that unblinding has occurred, the circumstances around the unblinding (eg, date, reason, and person performing the unblinding) must be documented promptly, and the Sponsor Clinical Director notified as soon as possible.

Once an emergency unblinding has taken place, the principal investigator, site personnel, and Sponsor personnel may be unblinded so that the appropriate follow-up medical care can be provided to the participant.

Participants whose treatment assignment has been unblinded by the investigator/medically qualified designee and/or nonstudy treating physician must be discontinued from study intervention, but should continue to be monitored in the study.

8.1.11 Calibration of Equipment

The investigator or qualified designee has the responsibility to ensure that any device or instrument used for a clinical evaluation/test during a clinical study that provides information about inclusion/exclusion criteria and/or safety or efficacy parameters shall be suitably calibrated and/or maintained to ensure that the data obtained is reliable and/or reproducible. Documentation of equipment calibration must be retained as source documentation at the study site.

8.2 Efficacy Assessments

Compliance with the efficacy assessments (along with study intervention use) is essential, and any non-compliance noted by the investigator or designee should result in consultation with the participant on corrective measures needed to ensure compliance.

8.2.1 Patient-reported Outcomes (PRO)

Each participant will be properly trained on CSD at Visit 1 and instructed on the PRO measurements at each visit. Participants will be contacted and reminded to complete the CSD as trained (eg, at telephone contacts).

Participants who discontinue study intervention early will continue to be monitored in the study and should be encouraged to continue to complete the PROs measures as outlined in the SoA.

8.2.1.1 Leicester Cough Questionnaire (LCQ)

Participants will be asked to complete the 19-item LCQ to assess the impact of their cough severity on physical, social and psychological functioning.

Participants will be complete the LCQ at study site visits outlined in the SoA

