8.10.5 Discontinued Participants Continuing to be Monitored in the Study

If a participant is discontinued from the study intervention early, the Discontinuation Visit assessments are to be performed as soon as possible.

It is intended that all participants should be followed through completion of the study, regardless of premature discontinuation of intervention unless the participant withdraws consent. Thus, participants who discontinue from study intervention prior to completion of the study should continue to be monitored to obtain relevant information through the end of the study. Study site visits/telephone calls should be made at timepoints that correspond to each remaining study visit. The follow-up information, limited to AEs, concomitant medication use, and patient report outcomes (site visits only) will be collected as outlined in the SoA.

Concomitant therapies specifically prohibited (see Section 6.5) while the participant was on study intervention are no longer prohibited after discontinuation of study intervention.

For these participants who have discontinued study intervention early, sites will be instructed to exert diligent efforts to continue to contact them. To enable sites to reach participants, the participants should provide primary and secondary contact information (eg, home telephone, work telephone, mobile telephone). Sites must document the outcome of the telephone contact(s), to demonstrate diligent efforts have been made. If a participant does not agree to be contacted for follow-up for each of the remaining visits (as described in Section 7.1), the participant should be encouraged to accept a telephone contact at least at Visit 8 date.

Additionally, the ICF will explain the importance of continued data collection from participants, including the use of continued contact by telephone.

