3.6.1 Statistical Methods for Efficacy Analyses

The analysis of efficacy endpoints will be based on the FAS population. Unless specified otherwise, analyses will include all follow-up efficacy data collected for those participants who discontinued treatment.

The continuous endpoints will be analyzed using the longitudinal analysis of covariance (ANCOVA) model. In this model, response variable will be change from baseline. The model will include terms for treatment, visit, and the interaction of treatment by visit and baseline value as a covariate. Visit is treated as a categorical variable so that no restriction is imposed on the trajectory of the means over time. An unstructured covariance matrix will be used to model correlations among repeated measures. If the unstructured covariance structure fails to converge with the default algorithm, then the AR(1) structure can be used to provide initial values of the covariance parameters. This model uses the maximum likelihood principle to estimate the parameters and account for missing data in an implicit fashion. The change from baseline to each visit and 95% CIs will be estimated from this model. Baseline variable is defined as the last non-missing value prior to the treatment.

Categorical endpoints will be analyzed by calculating the percentage of participants in each response category at each timepoint. For some endpoints (change from baseline in LCQ total score, change from baseline in mean weekly CSD total score), percentage of participants meeting certain threshold values will also be provided. Only observed data will be included in the analysis.

Considerations for the analysis specific to the respective endpoints are provided below.

LCQ total score

Change from baseline in the LCQ total score will be analyzed using the longitudinal ANCOVA model above to estimate within-treatment change from baseline and corresponding 95% CI at each time point. Percentage of participants who had an increase in the total score of ≥ 1.3 points from baseline at each time point will also be summarized.

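### After the Discontinuation Visit, participants who stop study drug and are followed only by telephone give no further LCQ, EQ5D-5L or PGIC, because off-drug PROs are tied to site visits and no remote route is provided

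*Combined protocol and SAP*

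**What the plan says.** Protocol 8.2.1.1 says of the LCQ: "Participants will be complete the LCQ at study site visits outlined in the SoA". Sections 8.2.1.3 and 8.2.1.4 say the same of the EQ5D-5L and PGIC. The Schedule of Activities (1.3) places these forms at numbered visits and in the discontinuation column, never at a telephone contact. The CSD is filled in each evening away from the site, but 8.10.4 has participants bring it to their visits, and the schedule shows no CSD in the discontinuation column.

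For participants who stop drug early, 8.10.5 first requires a visit: "Discontinuation Visit assessments are to be performed as soon as possible". After that, "Study site visits/telephone calls should be made at timepoints that correspond to each remaining study visit". What is collected is set out as follows: "The follow-up information, limited to AEs, concomitant medication use, and patient report outcomes (site visits only) will be collected as outlined in the SoA". If the participant will not agree to contact at each remaining visit, "the participant should be encouraged to accept a telephone contact at least at Visit 8 date". Section 8.2.1 adds that such participants "should be encouraged to continue to complete the PROs measures as outlined in the SoA".

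On the analysis side, sSAP 3.6.1 states that, unless specified otherwise, "analyses will include all follow-up efficacy data collected for those participants who discontinued treatment". Missing continuous values are left to the likelihood model. The responder percentages and the PGIC use observed data only.

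**The concern.** The secondary objective is LCQ change at Week 12 and through Week 52, and the plan expects nearly half of participants to stop drug before Week 52. The protocol goes to some length to stay in contact with them, and the sSAP means to use their off-drug efficacy data. The collection rule nevertheless lets a site keep in touch by telephone for months without obtaining another LCQ.

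The loss is unlikely to be random. People who stop because of side effects or lack of benefit have the least reason to travel to the site. If their cough-related quality of life falls back after stopping, the later estimates lean on people who stayed on drug or kept attending. The longitudinal model has no term for being off drug, so it can anticipate the fall only through a participant's own earlier scores and through other stoppers who still attend. The percentages with an LCQ gain of at least 1.3 points, the CSD responder percentages and the PGIC percentages have no model behind them: telephone-only participants simply leave the denominator.

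**Working it through.** **1. Reproduce the plan's figures (protocol 9.9, sSAP 3.9).**
- Completers: 160 × (1 − 0.47) = 84.8; the plan states 84. Expected early stoppers: 160 − 84 = 76 (47.5%).
- LCQ interval, 3.7 ± 1.96 × 3.9/√n: for n = 84, ± 0.83, giving (2.87, 4.53); for n = 42, ± 1.18, giving (2.52, 4.88). Both match the stated (2.9, 4.5) and (2.5, 4.9).

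The plan's precision is calculated on completers only, so losing off-drug LCQs does not take it below plan. What is at risk is bias.

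**2. Trace what a telephone-only stopper contributes.**
- Before stopping: every on-drug LCQ, all kept in the model.
- At the Discontinuation Visit: LCQ, EQ5D-5L and PGIC are scheduled, CSD is not. Under the sSAP appendix an LCQ counts as Week 52 from Day 316, and an EQ5D-5L or PGIC from Day 267. A visit before those days falls into an earlier window. LCQ recall is two weeks (protocol 4.2.1.2), so an LCQ taken promptly after the last dose mostly describes time on drug.
- Afterwards: AEs and concomitant medication by telephone. No PRO is scheduled at a call, and no section provides for completion or return away from the site.

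**3. Size the effect at Week 52.** The documents do not give the share f of the 76 stoppers who are telephone-only, nor the off-drug change c. Both are assumptions. The Week-12 figures (change 3.7, SD 3.9) are carried to Week 52, also as an assumption, and each telephone-only stopper is taken to have no LCQ in the Week-52 window.

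True mean = (84 × 3.7 + 76c)/160. Observed mean = (84 × 3.7 + 76(1 − f)c)/(160 − 76f). The overstatement is observed minus true.

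| f | LCQs lost | n observed | overstatement, c = 0 | overstatement, c = 1.85 | c = 3.7 | CI half-width |
|---|---|---|---|---|---|---|
| 25% | 19 | 141 | 2.20 − 1.94 = 0.26 | 2.95 − 2.82 = 0.13 | 0 | 0.64 |
| 50% | 38 | 122 | 2.55 − 1.94 = 0.61 | 3.12 − 2.82 = 0.30 | 0 | 0.69 |

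The half-width is 1.96 × 3.9/√n for both groups combined; with all 160 observed it would be 0.60. At the limit f = 100% (76 lost, n = 84), the overstatement is 1.76 for c = 0 and 0.88 for c = 1.85. These are shifts in the simple observed mean. Under the longitudinal model they shrink to the extent that earlier LCQs predict later ones.

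**The case against.** The strongest reply is that the protocol already asks for what is needed. Site attendance is the intended course, continued PRO completion is encouraged, and every early stopper is due a Discontinuation Visit with an LCQ. The site-visit restriction may only repeat the schedule's division between visits and calls. The single call at the Visit 8 date is for people who refuse repeated contact, and they may not return forms either. The LCQ is a secondary endpoint in a trial with no hypotheses and no planned between-group comparison, while the primary endpoint, AEs, is captured by telephone.

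Much of this stands, and it rules out some stronger readings:

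- A reader might infer that telephone-only participants give no LCQ at all. They do: their on-drug LCQs remain, and one is scheduled at the Discontinuation Visit.
- A reader might infer that the protocol and sSAP contradict each other. They do not: the sSAP commits only to data that were collected.
- A reader might infer a bias of a full point. With f = 60% and missing values filled at the full on-drug level, 45.6/160 × 3.7 = 1.05. That is an upper bound on an unsourced share, and it ignores each participant's own earlier scores.
- A reader might assume that the forms are on paper. No section says so.

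What does not fall is the gap itself. Whatever the purpose of the restriction, 8.10.5 allows contact by telephone and supplies no route for a PRO from someone contacted that way.

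**Conclusion.** The point holds as a gap in data collection and is best labelled a cheap improvement. After the Discontinuation Visit, a stopper followed only by telephone contributes no further LCQ, EQ5D-5L or PGIC and cannot hand in the CSD, although the sSAP would use all of them.

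The ceiling is about 76 of 160 participants. The number actually affected cannot be derived from the documents. It will be smaller because some stoppers will attend, some will have a Discontinuation Visit inside the Week-52 window, and some very early stoppers may fall outside the FAS, which needs a post-baseline observation during treatment. With 25% to 50% telephone-only and an off-drug change of 0 to 1.85 points, the simple observed Week-52 mean is overstated by about 0.13 to 0.61 points. That is below the matching CI half-widths (0.64 and 0.69) and below the 1.3-point important change, but not negligible at the upper end. It is less under the longitudinal model to the extent that earlier scores carry information, and zero if stopping drug does not change the LCQ. Stated precision and the primary safety endpoint are untouched.

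**What to change.** In 8.10.5, with matching wording in 8.2.1.1, 8.2.1.3 and 8.2.1.4, state that a participant who has discontinued study intervention and does not attend a site visit, but accepts contact, may complete the same LCQ, EQ5D-5L and PGIC, and the one-week CSD, at home and return them. Apply this at each remaining PRO time point, and at least at Week 12 (if not yet reached) and Week 52. Use the telephone contact at the Visit 8 date as the prompt for the Week-52 forms. Record the date and place of completion on the CRF. The return route should suit whatever medium the forms use.

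The sSAP needs little change, because 3.6.1 already takes in off-drug data that were collected. Its appendix ties the CSD analysis week to the day of the study visit, so one line should say which date takes its place when there is no visit.

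The cost is protocol wording, the added CRF items and minor logistics. Some forms will be completed at home rather than at the site, which mixes settings; the forms remain self-completed and the CSD is already done away from the site. Some will not be returned, so the gap narrows rather than closes. No visit is added.

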8.2.1.2 Cough Severity Diary (CSD)

Participants will be asked to record their cough frequency, intensity and disruption due to cough using the 7-item CSD. Participants will rate each item using an 11-point scale ranging from 0 to 10 with higher scores indicating greater severity.

Participants will complete the CSD, daily every evening beginning in the evening on the day of Visit 1 to the day before Visit 2 (for a minimum of 7 days between Visit 1 and prior to Visit 2). For Visit 3, 4, 5, 6, 7, and 8, the CSD will be completed every evening beginning 1 week prior to the visits. Participant should be contacted (eg, by telephone) around 1 week prior to those visits to remind them to complete the CSD during these weeks.

8.2.1.3 EuroQoL 5 Version Five Dimensions Questionnaire (EQ5D-5L)

The EQ5D-5L is a standardized instrument for measuring generic health status used for estimating preference weights for that health status. The participant will be asked to indicate their health state using a 5-level rating scale. The participant will also be asked to complete the EQ VAS to record the participant's self-rated health on a vertical VAS.

Participants will complete the EQ5D-5L at the study site visits outlined in the SoA.

8.2.1.4 Patient Global Impression of Change (PGIC)

Participants will be asked to rate the change in their chronic cough compared to the start of the study using the PGIC with response options ranging from “very much improved” to “very much worse”.

Participants will complete the PGIC at the study site visits outlined in the SoA.

8.3 Safety Assessments

Details regarding specific safety procedures/assessments to be performed in this study are provided below. The total amount of blood volumes drawn can be found in Section 8.

Planned time points for all safety assessments are provided in the SoA.

8.3.1 Chest Radiography/Computed Tomography Thorax Scan

A chest radiograph or computer tomography scan of the thorax should be performed locally for participants, at Screening, if this has not been done within the last 5 years and after the onset of chronic cough. The chest radiograph or computer tomography scan of the thorax should not demonstrate any abnormality considered to be significantly contributing to the chronic cough or any other clinically significant lung disease in the opinion of the investigator (see inclusion criterion 1, Section 5.1).

8.3.2 Physical Examinations

A complete physical examination will include assessments of the following general appearance; skin and lymphatic; eyes, ears, nose, throat; cardiovascular system; respiratory system; abdomen/gastrointestinal system; urological system; musculoskeletal and neurological systems. Other body systems may be examined.

A brief directed physical examination may be performed as outlined in the SoA except for Visit 1. A physical exam (complete or directed) can be performed at any unscheduled visit if deemed necessary by the investigator.

Clinically significant changes identified after randomization will be recorded as AEs in the eCRF.

Investigators should pay special attention to clinical signs related to previous serious illnesses.

8.3.3 Vital Signs and Weight and Height Measurements

Vital sign measurements, including systolic blood pressure (mm Hg), diastolic blood pressure (mm Hg), heart rate (beats per minute), respiratory rate (breaths per minute), and body temperature (in centigrade) will be collected as outlined in the SoA. All blood pressure measurements should be performed on the same arm at the same position, preferably by the same person. All body temperature should be measured by the same method.

Height (cm) and weight (kg) will also be collected as per the SoA

Any clinically significant abnormalities in vital signs and changes in weight identified after randomization will be recorded as AEs in the eCRF.

8.3.4 Electrocardiograms

A 12-lead electrocardiogram (ECG) will be obtained at Visit 1 using local standard procedures.

8.3.5 Spirometry

A spirometry assessment will be performed locally at Visit 1 using a calibrated spirometer. Assessments will include FEV₁, FVC, and FEV₁/FVC ratio.

Spirometry performed within the past year of Visit 1 and after the onset of chronic cough is acceptable if the investigator confirms that spirometry was done during a period where the participant was clinically stable (eg. not during an upper respiratory infection).

8.3.6 Clinical Safety Laboratory Assessments

- Refer to Appendix 2 for the list of clinical laboratory tests to be performed and to the SoA for the timing and frequency.
- The investigator must review the laboratory report, document this review, and record any clinically relevant changes occurring during the study in the AE section of the case report form (CRF). The laboratory reports must be filed with the source documents. Clinically significant abnormal laboratory findings are those which are not associated with the underlying disease, unless judged by the investigator to be more severe than expected for the participant's condition.
- All protocol-required laboratory assessments, as defined in Appendix 2, must be conducted in accordance with the laboratory manual and the SoA.
- If laboratory values from nonprotocol specified laboratory assessments performed at the institution's local laboratory require a change in study participant management or are considered clinically significant by the investigator (eg, SAE or AE or dose modification), then the results must be recorded in the appropriate CRF (eg, SLAB).
- For any laboratory tests with values considered clinically significantly abnormal during participation in the study or within 14 days after the last dose of study intervention, every attempt should be made to perform repeat assessments until the values return to normal or baseline or if a new baseline is established as determined by the investigator.

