4.3.3 Rationale for Dose Interval and Study Design

In this study, MK-7264 will be orally administered as MK-7264 45 mg BID or 15 mg BID based on the safety and pharmacokinetic efficacy results observed to date (refer to the IB).

Based on pharmacokinetic studies, MK-7264 is rapidly absorbed with a median time to reach maximum plasma concentration (T_{max}) of 1.0 to 2.0 hours. In addition, the half-life of MK-7264 is approximately 7 to 10 hours and consistent with a BID dosing schedule.

The duration of treatment is up to 1 year in order to provide a more robust assessment of the long-term safety, tolerability and efficacy of MK-7264 in the treatment of refractory or unexplained chronic cough.

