8 STUDY ASSESSMENTS AND PROCEDURES

- Study procedures and their timing are summarized in the SoA.
- Adherence to the study design requirements, including those specified in the SoA, is essential and required for study conduct.
- The investigator is responsible for ensuring that procedures are conducted by appropriately qualified or trained staff. Delegation of study site personnel responsibilities will be documented in the Investigator Study File Binder (or equivalent).
- All study-related medical (or dental) decisions must be made by an investigator who is a qualified physician (or dentist when appropriate).
- All screening evaluations must be completed and reviewed to confirm that potential participants meet all eligibility criteria. The investigator will maintain a screening log to record details of all participants screened and to confirm eligibility or record reasons for screening failure, as applicable.

- Procedures conducted as part of the participant's routine clinical management (eg, blood count) and obtained before signing of ICF may be utilized for screening or baseline purposes provided the procedure met the protocol-specified criteria and were performed within the time frame defined in the SoA.
- Additional evaluations/testing may be deemed necessary by the investigator and or the Sponsor for reasons related to participant safety. In some cases, such evaluation/testing may be potentially sensitive in nature (eg, HIV, Hepatitis C), and thus local regulations may require that additional informed consent be obtained from the participant. In these cases, such evaluations/testing will be performed in accordance with those regulations.

The standard amount of blood collected from each participant over the duration of the study will be approximately 50 mL (Appendix 2).

Repeat or unscheduled samples may be taken for safety reasons or for technical issues with the samples.

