8.1.8 Study Intervention Administration

Since MK-7264 45 mg and 15 mg will differ in appearance and have corresponding matching placebos, participants will receive two study intervention bottles for the treatment period (ie, either MK-7265 45 mg and placebo matched to MK-7264 15 mg OR MK-7264 15 mg and placebo matched to MK-7264 45 mg). Participant should be instructed to take one tablet from each bottle BID.

Participants will be provided with enough study intervention to last between study site visits. Prescription and distribution of study interventions are allowed at unscheduled visits as well as scheduled visits.

The first dose of study intervention will be administered at the study site at Visit 2 after completing baseline assessments. Subsequent dosing will be performed by the participant (ie, unsupervised at his/her home) BID, approximately 12 hours apart at approximately the same time each day. The last dose will be on the day before Visit 8.

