Appendix: Relative day ranges

Since it is not always possible for all study participants to come in for their clinic visits on the exact day specified in the protocol schedule, the following relative day ranges will be defined for each time point.

	Scheduled day	LCQ, CSD, vital signs	EQ5D-5L, PGIC, laboratory parameters	Body weight
Baseline	1	Day \leq 1	Day \leq 1	Day \leq 1
Week 4	28	2 \leq Day \leq 41	--	2 \leq Day \leq 55
Week 8	56	42 \leq Day \leq 69	--	--
Week 12	84	70 \leq Day \leq 125	2 \leq Day \leq 125	56 \leq Day \leq 125
Week 24	168	126 \leq Day \leq 216	126 \leq Day \leq 266	126 \leq Day \leq 266
Week 38	266	217 \leq Day \leq 315	--	--
Week 52	365	316 \leq Day	267 \leq Day	267 \leq Day

For the analysis of safety parameters, Day at post-baseline timepoints must be \leq 14 days following the last dose.
The analysis week for CSD will be defined based on the day of study visit by subjects. Seven (7) days to 1 day before the study visit will be used as the measurements for the analysis week to which the study visit day belongs.

If a subject has data on multiple days within a day range, the measurement closest to the scheduled day within the day range will be used in the analysis. If there are observations before and after the scheduled day that are equally apart from the scheduled day, then the observation after the scheduled day will be used for analysis. If two or more measurements are obtained on the same day, the average will be used as the observation for the day.

Baseline variable is defined as the last non-missing value prior to treatment. Typically this is the measurement taken at Visit 1 or Visit 2, depending on the endpoint.

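### The sSAP's nearest-day rule does not separate planned laboratory samples from repeats, so an abnormal visit value can be replaced by its own, sometimes off-drug, retest in the by-visit tables

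*Combined protocol and SAP*

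**What the plan says.** Protocol Section 8.3.6 covers laboratory values judged clinically significantly abnormal during participation or within 14 days after the last dose. For these, "every attempt should be made to perform repeat assessments until the values return to normal or baseline"; the investigator may also end the series by accepting a new baseline. No such rule applies to normal values. Section 8 separately allows other extra samples: "Repeat or unscheduled samples may be taken for safety reasons or for technical issues with the samples".

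The sSAP Appendix on relative day ranges decides which value represents a time point. When several fall in one range, "the measurement closest to the scheduled day within the day range will be used in the analysis". If two are equally distant, "then the observation after the scheduled day will be used for analysis". It adds: "If two or more measurements are obtained on the same day, the average will be used as the observation for the day". The Appendix draws no line between a planned sample and a repeat of it.

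The limit on off-treatment values begins "For the analysis of safety parameters, Day at post-baseline timepoints must be" and goes on to allow up to 14 days after the last dose. Protocol Section 8.1.8 fixes the end of dosing: "The last dose will be on the day before Visit 8". For laboratory data, sSAP Section 3.6.2 plans descriptive statistics of baseline, on-treatment and change values, plus clinical review. It specifies no shift table, worst-value summary or count beyond predefined limits.

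**The concern.** The two rules were written for different purposes and interact. The clinical rule generates extra samples because a result was abnormal, and continues until it has recovered or settled. The analysis rule then lets any of those samples stand for the visit if it lies nearer the scheduled day. Which value is tabulated therefore depends partly on the result itself and partly on whether the visit happened to be early.

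Two situations deserve attention. A retest after Visit 8 or after a Discontinuation visit is taken off drug, yet it can enter a summary labelled as on treatment. Protocol Section 4.3.3 says that "the half-life of MK-7264 is approximately 7 to 10 hours", so a week later (168 h / 10 h, about 17 half-lives at the slow end) the drug has gone. Discontinuers are also not rare in the planning: sSAP Section 3.9 assumes about 47%. Protocol Section 8.10.5 limits their later follow-up to adverse events, concomitant medication and patient-reported outcomes, so the Discontinuation visit may be their last planned laboratory sample.

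At stake is whether the by-visit laboratory tables show what was measured at the visits, in a study whose primary objective is safety and whose interim results support a regulatory filing (protocol Section 4.1).

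**Working it through.** The plan states no figure on this point, so there is none to reproduce. The check applies the sSAP selection rule to a visit sample and one later retest.

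**Inputs from the documents**
- Laboratory day ranges and scheduled days (sSAP Appendix): Week 12, Days 2 to 125, scheduled Day 84; Week 24, Days 126 to 266, scheduled Day 168; Week 52, Day 267 onward, scheduled Day 365.
- Recommended visit windows (protocol Section 1.3): Visit 5 ±4, Visit 6 ±7, Visit 8 ±14 days, giving 9, 15 and 29 possible visit days.
- Last dose: the day before Visit 8. Safety limit: 14 days after the last dose.

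**Assumptions, because the documents are silent:** visits spread evenly over those windows; one retest, L days after the visit; the retest enters the analysis dataset.

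**Condition.** Let d be the visit day minus the scheduled day. The retest is chosen when |d + L| < |d|, or when the distances are equal, since the later value wins. Both cases reduce to d ≤ −L/2. A visit on or after the scheduled day (d ≥ 0) never loses its value. After Visit 8 the retest falls L + 1 days after the last dose, so it qualifies only if L ≤ 13.

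**Visit days on which the retest replaces the visit value**

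| Retest lag L | Condition | Week 12 | Week 24 | Week 52 |
|---|---|---|---|---|
| 3 days | d ≤ −2 | 3/9 (33%) | 6/15 (40%) | 13/29 (45%) |
| 7 days | d ≤ −4 | 1/9 (11%) | 4/15 (27%) | 11/29 (38%) |
| 13 days | d ≤ −7 | 0/9 | 1/15 (7%) | 8/29 (28%) |
| 14 days | d ≤ −7 | 0/9 | 1/15 (7%) | 0/29 (14-day limit) |

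**Example.** Visit 8 falls on Day 351 and is abnormal; the last dose was on Day 350; a retest on Day 364 is normal. The retest is 1 day from Day 365 and the visit sample 14 days. The retest is exactly 14 days after the last dose, so it qualifies and becomes the Week 52 value.

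**Discontinuation visits.** Assume the last dose was the day before the visit, L = 7, and no other sample in the range. The same condition gives replacement for Discontinuation visits on Days 3 to 80 (Week 12), 126 to 164 (Week 24) and 267 to 361 (Week 52).

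**Effect on a mean.** Suppose a displaced value and its retest differ by 3 SD (an assumption). Using the planned completer numbers, one displacement moves the mean by 3/84 = 0.04 SD in the combined group or 3/42 = 0.07 SD in one arm; two displacements among 84 move it by 6/84 = 0.07 SD. A maximum or minimum can change outright.

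**The case against.** The strongest reply is that the abnormality is recorded elsewhere. Section 8.3.6 itself tells the investigator to enter clinically relevant laboratory changes as adverse events. Protocol Section 10.3.1 lists abnormal laboratory results among qualifying events, and adverse events are a primary endpoint, counted up to 14 days after the last dose. Section 8.4.7 makes a combined liver pattern a separate event of clinical interest. This stands: a reader might infer that drug-related abnormalities would be lost from the safety record, and the documents do not support that.

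Nor would participants vanish from a count of abnormal results, because no such count is planned.

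The direction is a tendency, not a certainty. Retesting may end at a new baseline that is still abnormal, and an early repeat may be worse than the original. Section 8 and Appendix 2 of the protocol also allow unscheduled tests that could replace a normal planned value with an abnormal one.

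It would also be too broad to call every Week 52 retest off drug. The laboratory range opens at Day 267, so a retest before Visit 8 may be on drug; only one after Visit 8, or after stopping treatment, must be off it.

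Finally, the documents do not say whether repeats enter the analysis dataset; data-management procedures are provided separately. That is fair, but nothing in the sSAP excludes them, and the selection rule as written would use them. Likewise, averaging with a technically faulty sample matters only if that sample yields a reported value.

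**Conclusion.** The point holds, at low severity. Followed as written, the sSAP can replace a planned or Discontinuation-visit laboratory value with its own retest whenever the first sample precedes the scheduled day and the retest falls nearer to it or ties. Because abnormality triggers the repeats, this tends to pull the by-visit laboratory summaries, mainly their extremes, towards normal, and it admits off-drug values up to 14 days after the last dose.

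The frequencies in the working depend on evenly spread visits and an assumed retest lag, neither of which the documents give. With a 7-day lag they range from 11% of in-window visit days at Week 12 to 38% at Week 52. They apply only to participants whose result prompted a retest, and the documents give no rate for that. The distortion is confined to the by-visit laboratory tables. It does not show that the adverse-event analysis or the overall safety conclusion is biased.

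**What to change.** In the sSAP Appendix, add for laboratory parameters:

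1. The nearest-day rule applies only to samples from planned visits, including the Discontinuation visit.
2. A repeat or other unscheduled sample is used only when the planned sample is missing or technically invalid.
3. A repeat is not averaged with the original.
4. Repeats are shown in listings.

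This needs a few sentences and a programming flag that separates planned from unscheduled samples. It requires no new data and leaves the retesting procedure untouched. The downside is that by-visit extremes may look slightly less favourable.
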